- 2.) Conduct a pilot study on the long-term efficacy for weight loss from endoscopic revision of the gastrojejunostomy anastomosis.

At The Society of American Gastrointestinal and Endoscopic Surgeons (SAGES) 2012 meeting, [name] and colleagues from South America reported their abstract on Endoscopic Revision of RYGB with a Suturing Device. The suturing device was the Apollo EndoSurgery OverStitch™. Fifteen patients underwent revision of the gastrojejunostomy by reducing the size of the anastomosis and all the patients reportedly did well at 12-month follow-up. Unfortunately, the details of this study were never published. We aim to replicate this study and report the 2 year weight loss profile. We have successfully completed 20 procedures with no major complications or deaths. However, due to the learning curve, we didn't perfect our technique until 6th patient. Thus, we would like to recruit another additional 20 patients to see if we can demonstrate a clear benefit in weight loss.

Inclusion Criteria:

All adult patients (>18 years old) who have previously undergone a Roux-en-Y gastric bypass (RYGB) and failed to lose 50% of their excess body weight two years after their RYGB will be considered candidates. Furthermore, patients will need to show no gastrointestinal (GI) abnormalities during the initial endoscopy and upper GI small bowel follow-through series. We will follow the general criteria for bariatric surgical revision where patients with a gastrojejunostomy stoma > 2 cm in diameter and/or gastric pouch volume > 30 mL will be considered as candidates for this novel endoscopic procedure. Candidates will need to first undergo counseling by our dedicated bariatric dietitian where a diet and lifestyle modification plan will be set forth. The goal of this plan is to allow the patient to lose weight at a rate of 1-2 pounds per week. Patients will need to adhere to this regimen and follow-up with the dietitian once a month for weight check. Those who can demonstrate weight loss will continue on this plan. Patients who fail to lose weight for two consecutive months will then proceed to be evaluated for endoscopic intervention.

Exclusion Criteria:

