Both of the above procedures are invasive and a lot of times cannot be completed laparoscopically because of intra-abdominal adhesions from prior surgeries. Therefore, these will then be done in standard open fashion through a midline incision. There is higher postoperative morbidity and mortality. Therefore, we are proposing this endoscopic technique where we make the diameter of the food exit site smaller by placing sutures. Preoperatively, patient demographics, weight profile, preexisting comorbidities, failure of prior medical weight loss treatment, previous surgical details, and metabolic profile labs (cholesterol, diabetes, liver function, and kidney function) will all be recorded.

All patients will undergo preoperative evaluation by UCSF anesthesia-ran PREPARE clinic to determine their anesthesia risks. This is a pre-existing service that all surgical patients have to attend. The procedure would be performed under general anesthesia in the operative suite. An esophageal overtube (US Endoscopy, Mentor, OH) is positioned to grant continuous safe access to the stomach. The pouch and stoma size of the gastrojejunostomy (GJ) anastomosis is measured. The surgeon will then utilize the Apollo EndoSurgery OverStitch™ system to reduce the size of the stoma. The OverStitch™ is a cap-based suturing system that is mounted on a high definition therapeutic dual-channel endoscope (GIF-2T180; Olympus Medical Systems Corporation, Tokyo, Japan.)

The curved needle arm mounts to the tip of the endoscopic. These are re-loadable through the working channels of the endoscope thereby negating the need to withdraw and reinsert the endoscope. A GJ stoma or pylorus greater than 2 cm will be considered to be dilated based on previous defined studies in the literature. This will be measured visually. Simple interrupted 2-0 sutures polypropylene (PP) will be placed under direct visualization. We estimate that we will need 2 to 3 sutures to narrow the stoma to a diameter of 0.8 to 1.0 cm. This should create the feeling of early satiety hopefully leading to decreased caloric intake followed by weight loss. Current literature estimates nearly a mean 25% EWL.

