Patients will be followed with the current UCSF bariatric protocol. No special follow-up or exams will be required from the usual population. The current protocol entails that patients will be seen 1-2 weeks after discharge and then every 3 months the first year and then every 6 months thereon after. They are specifically instructed to avoid non-steroidal anti-inflammatory drugs to decrease ulcers and bleeding. They will also be discharged on Omeprazole or an equivalent to decrease the acid in their stomach. This will be taken for 3 months to decrease gastrointestinal ulcers and minimize bleeding and/or perforation. Patients will be placed on a thick liquid diet the first two weeks and can advance to pureed food after their first postoperative visit with their surgeon.

Signs and symptoms for post-procedural bleeding or perforation include, but not limited to, the following:

- Hematemesis
- Abdominal pain
- Melena
- Hematochezia

- Fever
- Nausea/Vomiting
- Tachycardia

Data collected will include post-procedural weight profile, resolution of pre-existing comorbidities, and metabolic profile labs (cholesterol, diabetes, liver function, and kidney function) will all be recorded. Patients will be queried on their satisfaction with this novel but expanding endoscopic suturing technique for weight loss.

Time Commitment: The current follow-up for patients who undergo any type of bariatric procedure at the UCSF Bariatric program is for the patient to follow-up every 3 months for the first year and subsequently every 6 months thereafter. These patients are seen in clinic where their weight and estimated daily caloric intake are recorded. Nutritional labs are monitored. Our proposed study will not deviate from this.

All patients will be screened by the bariatric surgeons to see if they would benefit from a gastric bypass revision. They will follow the current NIH guidelines for bariatric surgery. All patients will be given the standard informed consent. HIPPA guidelines will be strictly adhered.

Risks/Benefits:

There may be a slight risk of esophageal or gastric perforation but this risk is very low. We are using the standard Olympus Dual-Channel Endoscope which is similar to the endoscopes used by gastroenterology daily for both diagnostic and therapeutic purposes. The caliber of the endoscope is not bigger than the endoscopes we are already using here at UCSF.

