There may be a risk of poor weight loss but this should not be considered uncomfortable or life threatening. There may be a risk of nausea or vomiting from general anesthesia or the gastrojejunostomy or pylorus revision being too narrow causing obstructive like symptoms. Patients can have the sutures removed endoscopically if they desire. This can be done under conscious sedation instead of general anesthesia.

Data and Safety Monitoring Plan

All patients will be subjected to the same monitoring and safety like current bariatric patients. Our procedure is even less invasive than the current options. There are no other special requirements for patients undergoing endoscopic suturing for weight loss. Current bariatric surgeries are followed every 3 months in clinic during the first year and subsequently every 6 months thereon after. Clinic visits consists of the following:

Weight monitoring

Lab checks (drawn before clinic visit):

- CBC**
- Serum Iron**
- Serum Folate**
- Liver Panel – AST, ALT, alk phos, T-bili, Direct bili, Albumin**
- Vitamin B12**
- Serum Calcium**

Electrolytes**Cholesterol Panel****Fasting Blood Sugar****II. Statistical Analysis**

Pre-operative, peri-operative, and postoperative data consisting of patient demographics, preoperative and surveillance laboratory data, operative details, percentage of excess weight loss (% EWL), resolution of co-morbidities, morbidity and mortality will be collected prospectively. Paired t-tests were used to calculate statistical differences between preoperative and postoperative values (Microsoft Excel, Seattle, WA).

III. Background:

The Roux-en-Y gastric bypass (RYGB) is among the most-performed bariatric procedures in the United States. It is currently the gold standard for bariatric surgery in terms of resolution of co-morbidities and percentage excess weight loss (%EWL). However, despite very good results, this procedure has a failure rate of over 20% in maintaining weight loss. Postoperative weight loss failures can be defined in many different ways. One of the most accepted parameters involves the patients' ability to achieve and maintain 50% EWL. If a patient who has undergone RYGB does not achieve 50% or more EWL, a surgical revision procedure may be required.

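### The only stated test names no visit and no missing-weight rule, so a 2-year paired t-test would rest on the patients weighed at 24 months and be biased if attendance depends on response

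*Combined protocol and SAP*

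**What the plan says.** All references are to the combined protocol and SAP.

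- **Analysis.** Section II, Statistical Analysis, lists the data to be collected and then gives one method: "Paired t-tests were used to calculate statistical differences between preoperative and postoperative values (Microsoft Excel, Seattle, WA". No visit, visit window or primary variable is attached to it. No section gives an analysis population, a missing-weight rule or a sensitivity analysis.
- **Aim.** The text after Specific Aim 2 says "We aim to replicate this study and report the 2 year weight loss profile". It reports 20 completed procedures, says the technique was not perfected until the 6th patient, and continues: "Thus, we would like to recruit another additional 20 patients to see if we can demonstrate a clear benefit in weight loss".
- **Schedule.** The follow-up text under Procedure (Section I) says "patients will be seen 1-2 weeks after discharge and then every 3 months the first year and then every 6 months thereon after". From month 3 that gives weights at about 3, 6, 9, 12, 18 and 24 months.
- **Source of weights.** Time Commitment says "These patients are seen in clinic where their weight and estimated daily caloric intake are recorded". The follow-up text adds "No special follow-up or exams will be required from the usual population". The data list says "Data collected will include post-procedural weight profile".
- **Benchmark.** The Procedure text says "Current literature estimates nearly a mean 25% EWL", with no SD and no visit.
- **Later events.** Risks/Benefits lets patients have the sutures removed on request. Section III, Background, describes re-operation as standard care for recidivism after earlier bariatric procedures. Neither place says how weights after such events are analysed.

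**The concern.** The postoperative value in the test could be any of about six weights. With 20 procedures already done, the visit could be chosen after the data are seen.

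If the 24-month visit is used, as the aim implies, a paired t-test needs both values. Each patient without a 24-month weight drops out, and that patient's 6- or 12-month weight is not used. Attendance at routine clinics over two years may well be related to how the patient is doing.

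There is no control arm, so the size of the 2-year mean is the main efficacy result, and readers will set it beside the literature figure the protocol itself quotes. The extension cohort is also recruited to show a benefit, so the error rate of the test matters too.

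**Working it through.** The plan gives no alpha, power, SD or dropout allowance, so there is no figure of its own to reproduce. What follows shows size under stated assumptions.

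**Inputs.** From the documents: n = 20 per cohort (40 pooled) and a mean of about 25% EWL. Assumed: SD 20 EWL points at 24 months; loss of 20% or 40%; log-odds of loss changing by 1 per SD of response (strong dependence); normal data; two-sided 5% test. Loss depends either on the 24-month value itself or on the 12-month value, whose correlation with month 24 is taken as 0.85² = 0.72.

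**Standard error with full data.** 20/√20 = 4.5; 20/√40 = 3.2.

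**Bias of the returners-only mean (simulated).**

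| Loss | Depends on 12-month value | Depends on 24-month value |
|---|---|---|
| 20% | 2.5 | 3.5 |
| 40% | 4.8 | 6.7 |

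The sign is plus if poor responders are lost and minus if good responders are. A closed form agrees in scale: bias = SD × ρ × φ(c)/r, where r is the share attending, c = z(1−r) and ρ is the correlation of attendance with response. With SD 20 and ρ = 0.5 it gives 3.5 at r = 0.8 and 6.4 at r = 0.6. It is zero at ρ = 0. The bias scales with the SD and does not depend on the true mean.

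**Rejection of no change by the returners-only paired t-test.** Unlike the bias, this depends on the true mean.

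| True mean, who is lost, share lost | n=20 | n=40 |
|---|---|---|
| 0, poor responders, 20% | 8–10% | 11–17% |
| 0, poor responders, 40% | 12–21% | 21–40% |
| 15, good responders, 40% | 31–39% | 57–69% |
| 25, good responders, 40% | 86–90% | above 99% |

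The first two rows should be 5%. For the third row, losing 40% at random would give 64–67% (n=20) or 93% (n=40), so part of the fall from the full-data 88–91% at n=20 is loss of numbers alone.

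**Does using the earlier weights help?** A likelihood estimate from two visits (12 and 24 months) lowers the root mean squared error at n=40 from 4.2–4.8 to 3.4–3.7 at 20% loss, and from 6.2–7.7 to 3.8–4.9 at 40%. A three-visit unstructured model (6, 12 and 24 months) beat the returners-only mean on this measure in all 44 simulated settings. In one, with a true mean of 15, variance growing over time, n=40 and 40% loss on the 12-month value, the returners-only mean was 20.4 with 72% interval coverage, and the model gave 15.0 with 95%.

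**Covariance parameters.** k visits need k(k+1)/2: 6 for three visits, 10 for four. With n=20 and 40% loss, 20 × 0.6 = 12 patients have a 24-month weight.

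**Zero-change sensitivity.** The mean is (1 − loss) × (15 ± bias). At 20% loss this is 0.8 × (15 ± 3.46) = 9.2 to 14.8. At 40% it is 0.6 × (15 ± 6.65) = 5.0 to 13.0. With loss unrelated to response it is 12.0 and 9.0.

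**The case against.** This is a one-arm pilot on feasibility, and its first aim is to describe a technique. The plan promises a weight profile from scheduled visits, so earlier weights need not go unreported; only the 24-month test would ignore them. No attendance rate or SD is documented, and at 20% loss the bias is below one standard error at n=20 and about one at n=40. A mixed model on a dozen 24-month weights may look excessive.

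Much of this stands. It limits the size of the point and argues for the three-visit model over a four-visit one, which was examined only at 40% loss. It does not supply the missing visit or rule, and the recruitment of 20 more patients to show benefit is an efficacy purpose.

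Three stronger readings are tempting and are not supported:

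- **That the 2-year result will be overstated.** The direction depends on who stays away, and the documents are silent on that.
- **That the test is either safe or ruined.** If poor responders are lost and the true change is zero, false rejection rises. If the true mean is near the quoted 25% EWL, power remains high even when good responders are lost.
- **That the protocol foresees re-operation after failed suturing.** Section III describes recidivism after earlier bariatric procedures, which is the population being enrolled. Re-operation after failed suturing is an inference.

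**Conclusion.** The omission is plain in the text and worth correcting, as a should-fix point. The 24-month visit is in the schedule; what is missing is its designation in the analysis and a rule for patients not weighed then. The bias statement is conditional and runs both ways.

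The sizes rest on an assumed SD of 20 and strong response-related loss; weaker dependence or better attendance shrinks them, to zero if attendance is unrelated to response. The power figures of 31–39% and 57–69% also rest on an assumed true mean of 15, which is not in the documents. The effect of leaving the visit open to choice was not quantified.

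**What to change.** 1. Name change in weight (% EWL) from procedure day to 24 months as the single primary weight contrast. Treat other visits as descriptive.
2. Report the number weighed at each visit, and search the chart for a weight near 24 months when that visit is missed.
3. Estimate the 24-month mean on all treated patients with a repeated-measures mixed model on the 6-, 12- and 24-month weights, with visit as a category and unstructured covariance. Add month 18 only if numbers allow. Show the returners-only paired t-test beside it.
4. Add a sensitivity analysis that sets missing 24-month change to zero.
5. Report how many patients had sutures removed or a later surgical revision. Give the 24-month result including their later weights as the main result and excluding them as a sensitivity result, noting that exclusion may itself select out failures.
6. Show results separately for the early learning-curve patients when the two cohorts are pooled.

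**Cost.** SAP wording, standard statistical software in place of Excel, and a chart search; no new visits. The zero-change figure will look less favourable. The model reduces but does not remove bias from loss that depends on the unseen 24-month weight: in the four-visit version at 40% loss, 2.0–3.7 points remained of 6.6–6.8.

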Surgical revisions after RYGB are, by nature, complex, and associated with significant morbidity and even questionable efficacy. Among possible causes of RYGB procedure failure is dilation of the gastro-jejunostomy (GJ) and/or gastric pouch enlargement. The development of endoluminal therapies and devices for stoma revision can fulfill the need for a less-invasive approach that maintains some of the principles of surgical outlet revision while avoiding intra-abdominal surgery. As the number of bariatric surgeries, including RYGB, increases into the hundreds of thousands annually, it is natural that weight loss failure rates will also increase proportionally. The reported RYGB failure rate varies widely, from less than 10 percent to 50 percent, depending on the assessment parameters.

Patients who have regained weight to a condition of morbid obesity while under multidisciplinary surveillance should consider revision surgery. A revision on an RYGB procedure can be done on its restrictive component (the gastric pouch and the GJ) or at its malabsorptive/metabolic component (bowel limb lengths). Surgical revisions of the RYGB are always a matter of concern due to higher rates of complications and mortality when compared with primary series. This require re-entering a previously operated field, either laparoscopically or open, where the anatomy is distorted and view is obscured from dense intra-abdominal adhesions.

One potential solution is to avoid from having to enter the abdomen all together and perform the revisions endoscopically. Endoscopic suturing to narrow the gastrojejunostomy will increase the transition time for food to pass through resulting in early satiety and decreased caloric absorption. The Apollo EndoSurgery OverStitch™ is the latest endoscopic suturing system approved by the FDA for minimally invasive endoscopic therapies.

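### The only stated analysis of the surveillance labs is a paired t-test of the mean, which is insensitive to silent harm in two or three patients

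*Combined protocol and SAP*

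**What the plan says.** Section II has two sentences. The first lists what is collected, including "preoperative and surveillance laboratory data, operative details", percentage excess weight loss, comorbidity resolution, morbidity and mortality. The second gives the only method: "Paired t-tests were used to calculate statistical differences between preoperative and postoperative values". It sets no abnormality limit, shift table, per-patient count, grading or listing.

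The Data and Safety Monitoring Plan lists the clinic labs: CBC, iron, folate, B12, calcium, electrolytes, a liver panel with albumin, cholesterol and fasting glucose. It gives no rule for summarizing them. The Procedure part of Section I says only "Nutritional labs are monitored". The labs it names as recorded before and after the procedure are narrower: "metabolic profile labs (cholesterol, diabetes, liver function, and kidney function) will all be recorded". CBC, iron, folate and B12 are not named there.

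Bleeding is an anticipated risk. The Procedure part lists its warning signs, and says of the acid-suppressing drug: "This will be taken for 3 months to decrease gastrointestinal ulcers and minimize bleeding and/or perforation".

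**The concern.** Bleeding after a suturing procedure would be expected to affect some patients and leave most unchanged. A paired t-test asks whether the average patient changed. A few large falls move the average only slightly, and they also widen the SD by which the test divides. The test can therefore return a non-significant result while several patients have had a clinically notable fall.

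What is at stake is the reporting of laboratory safety, not the care of the individual, since results are seen at clinic visits. Morbidity is collected but not defined, so an abnormal hemoglobin, iron or B12 value in a patient without symptoms has no stated route into the results except through a mean. In a pilot of 20 to 40 patients, a non-significant mean says little about whether a few were harmed.

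**Working it through.** The documents give no alpha, SD, effect size or power, so there is no stated figure to reproduce.

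**Inputs from the documents.** n = 20 (first cohort) or 40 (with the additional 20 in Section I, Specific Aims). Method: paired t-test.

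**Assumptions, not in the documents.** Two-sided alpha 0.05; one postoperative value per patient; hemoglobin change normal with mean 0 and SD 0.7 or 1.0 g/dL in unaffected patients; k affected patients fall by a further D = 2 or 3 g/dL.

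**Step 1: limit without noise.** Suppose k of n patients fall by D and the rest do not change.
- Mean change = -kD/n
- Sample variance = D² k(n-k) / [n(n-1)]
- |t| = (kD/n) / sqrt(variance/n) = sqrt[k(n-1)/(n-k)]

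D cancels, so the size of the fall does not matter.

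| n | critical t | k=2 | k=3 | k=4 |
|---|---|---|---|---|
| 20 | 2.093 | 1.45 | 1.83 | 2.18 |
| 40 | 2.023 | 1.43 | 1.78 | 2.08 |

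For example, with n = 20 and k = 3, sqrt(3 × 19/17) = 1.83. In this limit three affected patients do not reach significance however far they fall; four do.

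**Step 2: with noise.** Simulated share of trials with a significant fall, over both SDs and both values of D:

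| Affected | n = 20 | n = 40 |
|---|---|---|
| 2 | 8-9% | 6-9% |
| 3 | 13-18% | 10-16% |
| 4 | 20-36% | 15-28% |
| 6 | 44-83% | 29-63% |

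The mean shift is kD/n. For 3 of 20 it is 3 × 2/20 = 0.30 to 3 × 3/20 = 0.45 g/dL.

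**Step 3: what a count would show.** If the count identified exactly the affected patients, the exact (Clopper-Pearson) 95% intervals would be:
- 2/20 = 10% (1.2-31.7%)
- 3/20 = 15% (3.2-37.9%)
- 4/40 = 10% (2.8-23.7%)
- 0 cases: upper limit 16.8% (n = 20) or 8.8% (n = 40)

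At a true risk of 10%, the chance of at least one case is 1 - 0.9^20 = 87.8% or 1 - 0.9^40 = 98.5%.

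**Step 4: false flags.** The schedule gives about 6 lab visits to 24 months (four in year one, two in year two). With a nominal 5% of values out of range per test and independent visits (assumptions), a rule of any value out of range flags 1 - 0.95^6 = 26% of unaffected patients per analyte. Two fixed visits, counting the adverse side only at 2.5%, flag 1 - 0.975^2 = 4.9%. The counting rule therefore has to be narrow.

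**The case against.** Several points on the other side stand, at least in part.

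- **Morbidity is collected.** The Procedure part lists the warning signs of bleeding, and a bleed large enough to lower hemoglobin by 2-3 g/dL may well be recorded as a complication. This stands. What remains is laboratory change without symptoms.
- **Nutritional deficiency.** A reader might infer that the t-test would hide deficiency as well. The documents do not support that as a general statement. Section III says the narrowing "will increase the transition time for food to pass through resulting in early satiety and decreased caloric absorption", an effect intended in every patient and stated for calories, not for iron or B12. A shift across the group is what a paired t-test can find: a 0.5 SD shift has 56% power at n = 20 and 87% at n = 40. The calculation above covers only a fall confined to a few patients.
- **Harm at any rate.** A reader might also infer that harm in 10-15% of patients would nearly always be missed. At 15% of 40 (k = 6) it is missed in about 37-71% of trials, so masking is far from certain.
- **A claim of safety.** Nowhere does the plan say that a non-significant p-value will be taken as evidence of safety. Its one reported safety result is an event statement about the first 20 procedures. The risk lies in how the result would be read.
- **Coverage of the labs.** The t-test sentence does not name them, and baseline CBC, iron, folate and B12 are not listed as recorded. For these analytes the paired test may lack its pair. That leaves them with no stated analysis at all, which does not weaken the case for a per-patient summary.

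**Conclusion.** The point holds in limited form. For safety labs where harm may fall on a few patients, the one stated method has about a 6-18% chance of showing a significant fall when 2 or 3 of 20 or 40 patients are affected. The percentages rest on the assumed hemoglobin SDs and falls. The noise-free result for three or fewer patients does not depend on them. Sensitivity improves from 4 affected patients upward.

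The gap concerns silent laboratory change, and neither stated aim (technique and weight loss) is threatened. It is worth correcting because a count is better suited to the question and uses values already drawn.

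**What to change.** In Section II:

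1. Keep the paired t-test for weight and metabolic values, and as a description of mean laboratory change.
2. For the safety labs already drawn, name CBC/hemoglobin, iron, folate, B12 and albumin as key analytes, and record the preoperative value where one is available.
3. Per analyte, report the number and percentage of patients who move from within to outside the laboratory's reference range in the adverse direction at stated visits (for example 12 and 24 months), with exact 95% confidence intervals.
4. List each patient's baseline and worst values, and report patients without a baseline separately. The listing also shows large falls that stay within range.
5. State that a non-significant mean change is not evidence of safety.

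**Cost.** A few sentences and one tabulation, with no new tests, visits or staff. The intervals will be wide, and some out-of-range values will be unrelated to the procedure and cannot be attributed without a control arm.
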